9.6.3 Secondary Endpoints

Secondary endpoints are the following:

1. The proportion of subjects in clinical remission at Months 2, 4, and 6, defined as a score of 0 for rectal bleeding and 0 or 1 for stool frequency based on Clinical Response Score subset of the Clinical and Endoscopic Response Score
2. Time to relapse, defined as number of days from randomization to the day of withdrawal due to escalation of therapy (i.e., surgical therapy, use of steroids, immunosuppressive or immunomodulating drugs, biologics, increase dose of 5-ASA in any form)
3. The proportion of subjects with an increase from baseline in the Clinical and Endoscopic Response Score by 2 or more points in at least 1 component or by 1 or more points in at least 2 components at Month 6

4. The change from baseline in serum CRP levels at Months 2, 4, and 6
5. The change from baseline in fecal calprotectin levels at Months 2, 4, and 6
6. The change from baseline to each scheduled assessment for published and validated domain scores of the IBDQ
7. Safety assessed by incidence and severity of AEs and abnormal laboratory values

The proportion of subjects in clinical remission at Months 2, 4, and 6 will be analyzed by the generalized estimating equations approach as longitudinal binary outcomes. The model will include randomization strata, treatment, time, and treatment- by-time interaction. The clinical remission rates and odds ratios will be estimated for each time point.

The time to relapse will be analyzed by a log-rank test stratified by the randomization strata.

The change from baseline in serum CRP and fecal calprotectin levels will be assessed with a repeated-measures analysis of covariance (ANCOVA) model that includes randomization strata, treatment, time, and treatment-by-time interaction as fixed effects, and baseline value as a covariate based on the observed data. The adjusted changes from baseline and their difference between treatment groups will be estimated for each time point.

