9.6.4 Health-related Quality of Life

Change from baseline to each scheduled assessment will be summarized for published and validated domain scores of the IBDQ. The change from baseline in IBDQ scores will be assessed with a repeated-measures ANCOVA model that includes randomization strata, treatment, time, and treatment-by-time interaction as fixed effects and baseline value as a covariate based on the observed data.

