The change from baseline in serum CRP levels and fecal calprotectin levels at Months 2, 4, and 6 will be analyzed by repeated-measures analysis of covariance (ANCOVA) models that include the randomization strata, treatment, time, and treatment-by-time interaction as fixed effects, and the corresponding baseline value as a covariate. The adjusted changes from baseline and their difference between treatment groups will be estimated for each time point. The overall treatment difference over 6 months will be estimated as the main effect for treatment in the model. The missing values will be left as missing, and an unstructured correlation matrix will be assumed.

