9.4 Other Endpoint(s)

9.4.1 Health Related Quality of Life

The change from baseline in the IBDQ will be analyzed for the ITT analysis set.

The following domain scores for the IBDQ (Guyatt et al., 1989)(9) will be calculated by adding up scores from questions included in the domain for each subject at each time point:

- Bowel symptoms: Questions 1, 5, 9, 13, 17, 20, 22, 24, 26, 29
- Emotion function: Questions 3, 7, 11, 15, 19, 21, 23, 25, 27, 30, 31, 32

- Systemic symptoms: Questions 2, 6, 10, 14, 18
- Social function: Questions 4, 8, 12, 16, 28

The total score will be calculated by adding up all scores for each subject at each time point.

The handling of missing score in the calculation of the domain and total scores will be based on McMaster University (2010)(10). If there is only one missing response within a domain, the missing response will be imputed as an average of other responses within the domain. If there are two or more missing responses within a domain, the domain score will be considered missing.

If there are up to four missing responses, the missing responses will be imputed as an average of other responses. If there are more than four missing responses, the total score will be considered missing.

The change from baseline in the IBDQ domain and total scores at Months 2, 4, and 6 will be analyzed by repeated-measures ANCOVA models that include treatment, randomization strata, time, and treatment-by-time interaction as fixed effects, and the corresponding baseline value as a covariate. The adjusted changes from baseline and their difference between treatment groups will be estimated for each time point. The missing values will be left as missing, and an unstructured correlation matrix will be assumed.

10 Safety

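### The CRP, fecal calprotectin and IBDQ models force one baseline slope on Months 2, 4 and 6; letting it vary by month is a free improvement that protects Month 6 precision and guards against a small bias of unknown sign

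*Protocol*

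**What the plan says.** Four places specify the same mean model.

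- Protocol 9.6.3 (CRP, fecal calprotectin): randomization strata, then "treatment, time, and treatment-by-time interaction as fixed effects, and baseline value as a covariate based on the observed data".
- Protocol 9.6.4 (IBDQ): randomization strata, then "treatment, time, and treatment-by-time interaction as fixed effects and baseline value as a covariate based on the observed data".
- SAP 9.3 (CRP, fecal calprotectin): strata, treatment, time, then "treatment-by-time interaction as fixed effects, and the corresponding baseline value as a covariate".
- SAP 9.4.1 (IBDQ): "treatment, randomization strata, time, and treatment-by-time interaction as fixed effects, and the corresponding baseline value as a covariate".

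Baseline enters each model once, as a main effect. On output, SAP 9.3 says "The adjusted changes from baseline and their difference between treatment groups will be estimated for each time point", so a separate Month 6 contrast is a planned result. On missing data and covariance it says "The missing values will be left as missing, and an unstructured correlation matrix will be assumed". SAP 9.4.1 does the same for the IBDQ.

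Other provisions bear on the point:

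- Protocol 4.4 withdraws subjects whose colitis worsens enough to need stepped-up treatment.
- The note under protocol Table 1 has subjects who stop treatment complete the end-of-treatment visit. Section 6.2.5 includes CRP, calprotectin and IBDQ in that visit.
- SAP Table 2 assigns data from Day 141 onward to Month 6.
- SAP 9.3 calls CRP and calprotectin key secondary endpoints. SAP 9.1 applies no multiplicity adjustment to secondary tests.

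**The concern.** The plan lets the treatment effect differ by month and leaves the covariance free, yet it restricts the regression on baseline to be identical at weeks 8, 16 and 24. No reason is given. Baseline is taken in remission, before about half the subjects move to placebo, so it may well predict week 8 better than week 24. A common slope is then too steep at Month 6.

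Two consequences follow. First, the Month 6 comparison carries residual variation that the baseline adjustment should not have introduced. Second, the likelihood analysis of incomplete data relies on a correct mean model. If subjects still observed at Month 6 differ in baseline between arms, a wrong slope adjusts that difference by the wrong amount. The multiple-imputation and pattern-mixture analyses in SAP 9.2.2 cover only the primary endpoint, so nothing else in the plan would show either effect.

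**Working it through.** **The plan's own figure.** The only stated calculation concerns the primary endpoint: 68% vs 49%, 120 per group, two-sided 0.05. The pooled rate is 0.585. The null SE is √(2 × 0.585 × 0.415 / 120) = 0.0636 and the alternative SE is √((0.68 × 0.32 + 0.49 × 0.51) / 120) = 0.0624. Power = Φ((0.19 − 1.96 × 0.0636) / 0.0624) = Φ(1.05) = 85.2%. The stated 85% is reproduced. There is no corresponding figure for the repeated-measures models.

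**Assumed inputs.** Unit SDs; baseline slopes at Months 2/4/6 (with unit SDs, also the correlations with baseline) of 0.6/0.5/0.4, 0.6/0.4/0.2 or 0.7/0.4/0.1, with 0.5/0.5/0.5 as the no-fade case; residual correlation 0.3 to 0.6; 120 per arm. Strata are left out.

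**Precision, complete data.** Let b be the three true slopes and Σ the residual covariance, with variances 1 − b². Maximum likelihood settles on b* = (1′Σ⁻¹b)/(1′Σ⁻¹1). The Month 6 residual variance rises from 1 − b₆² to 1 − b₆² + (b₆ − b*)². The SD of the Month 6 difference is therefore multiplied by √(1 + (b₆ − b*)²/(1 − b₆²)).

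Example: slopes 0.7/0.4/0.1, residual correlation 0.3. The weights are 0.558, 0.254 and 0.188, so b* = 0.391 + 0.102 + 0.019 = 0.511. The factor is √(1 + 0.411²/0.99) = 1.082. The SE goes from √(2 × 0.99/120) = 0.129 to 0.139.

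| Slopes | Factor, residual corr. 0.3 | Factor, residual corr. 0.6 | Simulated SD, common slope vs baseline-by-time |
|---|---|---|---|
| 0.6/0.5/0.4 | 1.008 | 1.010 | 0.122 vs 0.121 |
| 0.6/0.4/0.2 | 1.031 | 1.042 | 0.128 vs 0.123 |
| 0.7/0.4/0.1 | 1.082 | 1.123 | 0.140 vs 0.129 |
| 0.5/0.5/0.5 | 1.000 | 1.000 | models agree |

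The simulated loss is about 0 to 8%. The formula reaches 12% only for the steepest fade with the higher residual correlation. With withdrawal added, the simulated SD was 1.5% to 15% larger when the slope faded.

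**Bias: mechanism.** To a first approximation, ignoring what earlier visits contribute through the covariance, bias in the Month 6 difference ≈ (b₆ − b*) × (mean baseline of mesalamine subjects still observed − mean baseline of placebo subjects still observed). With a fading slope the first factor is negative. With complete data the second is zero on average. If withdrawal follows a high marker level and is commoner on placebo, remaining placebo subjects have the lower baselines; the second factor is positive and the bias negative (toward mesalamine on CRP and calprotectin). If withdrawal follows a rise from the subject's own baseline, those who leave tend to have started low. The second factor changes sign, and so does the bias.

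**Bias: simulation.** Common slope minus baseline-by-time, large samples, true effects −0.2/−0.3/−0.4 SD, extra placebo withdrawal, Month 6 missing 42–44% placebo and 24–27% mesalamine:

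| Slopes | Residual corr. | Level-driven | Halfway mix | Change-driven |
|---|---|---|---|---|
| 0.6/0.5/0.4 | 0.3 | −0.017 | −0.002 | +0.017 |
| 0.6/0.5/0.4 | 0.6 | −0.020 | −0.002 | +0.018 |
| 0.6/0.4/0.2 | 0.3 | −0.034 | +0.003 | +0.033 |
| 0.6/0.4/0.2 | 0.6 | −0.041 | −0.002 | +0.038 |
| 0.7/0.4/0.1 | 0.3 | −0.068 | −0.005 | +0.049 |
| 0.7/0.4/0.1 | 0.6 | −0.076 | −0.012 | +0.053 |

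More withdrawal on mesalamine gave +0.013 to +0.043 SD. No treatment effect with the same withdrawal rule in both arms gave 0.000. With baseline-by-time fitted, bias was zero to within simulation noise (about 0.015 SD). The standard error at 240 subjects is about 0.12 to 0.18 SD.

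**The case against.** The strongest reply is that a baseline main effect is an ordinary prespecified ANCOVA form, that fading is not shown in the documents, and that the endpoints affected are secondary and carry no multiplicity-controlled claim. All of that stands, and it is why the point is low in severity.

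The plan also limits the missing data. Subjects who stop early should have the markers and IBDQ measured at withdrawal, and those who stop from Day 141 supply a Month 6 value. This helps but does not remove the problem. Earlier withdrawals still have no Month 6 value. Under the closest-day rule in SAP 9.1, a withdrawal visit on Day 70 would also lose the Month 2 slot to a visit already made on Day 56.

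A reader might infer more: that the plan favours mesalamine, or that it inflates type I error. The documents support neither.

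- **Direction.** A bias toward mesalamine needs withdrawal to track the absolute marker level and to be commoner on placebo. The withdrawal criterion in protocol 4.4 is about worsening, which can equally be read as change from the subject's own starting point, and then the sign reverses. The assumed 68% and 49% remission rates suggest more failures on placebo, but they are not withdrawal rates and do not identify the driver.
- **Error rate.** One set of null runs gave rejection up to 8.0% with correlations of 0.75/0.5/0.25 and 45% vs 22% missing. A drug with no effect would not produce that imbalance if withdrawal depended only on the marker; extra placebo withdrawal had to be imposed. Separate null runs with extra placebo withdrawal gave 5.4–5.7% for the common slope against 4.1–5.3% with the interaction. At 700 replicates the Monte Carlo SE is √(0.05 × 0.95/700) = 0.8 points, so that difference is close to noise.

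**Conclusion.** The point holds as a modest improvement to secondary analyses. All four model statements omit baseline-by-time, and month-specific differences will be reported from them.

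If the baseline slope fades, the Month 6 difference is less precise: roughly 0 to 8% in SD with complete data in the simulated patterns (12% at the formula's extreme) and about 0 to 15% with withdrawal. If, in addition, withdrawal depends on observed values and differs between arms, a small bias is possible. It is mostly under 0.08 SD, about 0.10 SD at most in the 240-subject runs, and below one standard error. Its sign cannot be determined from the documents.

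Every size given here rests on assumed slopes, correlations and withdrawal rates. With a constant slope there is nothing to correct. The primary remission analysis does not use these models and is not affected.

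**What to change.** Before unblinding, add the baseline-by-time interaction to the fixed effects in SAP 9.3 (CRP, fecal calprotectin) and SAP 9.4.1 (IBDQ). The terms become strata, treatment, month, treatment × month, baseline and baseline × month. Estimate the adjusted changes for both arms at the overall mean baseline at each month, and keep the unstructured covariance.

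Either align protocol 9.6.3 and 9.6.4 or record the change in SAP section 12, which now reports no departure from the protocol's analysis. Aligning the protocol would need an amendment under section 12.1; recording the change in the SAP avoids that.

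The cost is 2 degrees of freedom per model and no new data. With constant slopes the two models gave the same Month 6 SD (0.111 and 0.111 with complete data), so nothing measurable is lost if the baseline's influence does not fade.

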9.6.4 Health-related Quality of Life

Change from baseline to each scheduled assessment will be summarized for published and validated domain scores of the IBDQ. The change from baseline in IBDQ scores will be assessed with a repeated-measures ANCOVA model that includes randomization strata, treatment, time, and treatment-by-time interaction as fixed effects and baseline value as a covariate based on the observed data.

9.7 Extent of Exposure and Treatment Compliance

The length of the treatment, calculated as (last dose date – first dose date + 1 day), will be summarized by treatment group for the safety analysis set.

The overall compliance will be summarized for the safety analysis set.

9.8 Safety

9.8.1 General Considerations

Safety parameters will be evaluated for the safety analysis set.

9.8.2 Adverse Events

A ‘pre-treatment’ AE will be defined as an AE that occurs between screening and the first dose of the IMP. A ‘treatment-emergent AE (TEAE)’ will be an AE that occurs in the time interval from initial dosing (IMP intake) to the end of treatment visit. If an AE on Day 1 occurs before IMP intake, it will be recorded as a pre-treatment AE.

Written narratives will be issued for all SAEs and AEs leading to withdrawal. If causality is missing, the AE will be regarded as being reasonably possibly related to IMP. Related AEs (judged as being reasonably possibly related to IMP) will be termed adverse drug reactions (ADR).

An AE overview summary table will be prepared for the safety analysis population. It will display the number and percentage of subjects reporting an AE and the number of events reported for each treatment group. The following categories will be displayed:

- any TEAEs
- deaths
- SAEs
- AEs leading to discontinuation
- severe AEs
- ADRs

Number and percentage of subjects reporting the following types of TEAEs will be summarized by MedDRA SOC (alphabetically) and PT (in decreasing frequency of occurrence):

- any TEAEs
- common TEAEs
- causal relationship to IMP with reasonable possibility or no reasonable possibility
- intensity with mild, moderate, or severe
- AEs leading to death
- SAEs
- AEs leading to discontinuation

Supporting data listings will be provided for:

- all AEs sorted by trial site and subject ID
- all AEs sorted by MedDRA SOC and PT
- SAEs
- AEs leading to death
- AEs leading to discontinuation

9.8.3 Safety Laboratory Variables

Clinical laboratory variables will be presented in 2 ways. First, mean change from baseline to the end of the double-blind treatment visit will be summarized. Baseline will be defined as the last assessment before the first dose of IMP. Second, the number and percentage of subjects with

treatment-emergent potentially clinically significant laboratory values on or before the end of the double-blind treatment visit will be tabulated.

9.8.4 Other Safety Variables

Other safety assessments will be summarized descriptively.

9.9 Interim Analyses

No interim analysis is planned.

10 DATA HANDLING

10.1 Source Data and Source Documents

Source Data – International Conference on Harmonisation (ICH) Definition

Source data are defined as all information in original records and certified copies of original records of clinical findings, observations, or other activities in a clinical trial necessary for the reconstruction and evaluation of the trial. Source data are contained in source documents (original records or certified copies).

Source Documents - ICH Definition

Source documents are defined as original documents, data, and records (e.g., hospital records, clinical and office charts, laboratory notes, memoranda, subjects' diaries or evaluation checklists, pharmacy dispensing records, recorded data from automated instruments, copies or transcriptions certified after verification as being accurate copies, microfiches, photographic negatives, microfilm or magnetic media, x-rays, subject files, and records kept at the pharmacy, at the laboratories and at medico-technical departments involved in the clinical trial).

Trial-specific Source Data Requirements – Ferring

The investigator must maintain subject records, including as a minimum: medical history; data on the condition of the subject at the time the subject is enrolled into the trial in order to document (and enable verification of) subject eligibility; diagnosis; subject's participation in trial; subject's trial identification; date of informed consent and time, if applicable, for the trial; visit dates and results of examinations and tests performed, especially results of examinations related to primary endpoints; details of IMP administration; details of AEs, concomitant medication, and of any follow-up and analysis/tests/examinations done; and reason for subject withdrawal from the trial.

10.2 eCRF

An eCRF system provided by an independent, third-party Contract Research Organization (CRO) will be used for data capture. The system is validated and access at all levels to the system is granted/revoked following Ferring and vendor procedures, in accordance with regulatory and system requirements.

The eCRF system and the database will be hosted at the independent, third-party CRO. After the trial database is declared clean and released to the statistician, a final copy of the database will be stored at Ferring Pharmaceuticals A/S located in DK-2300 Copenhagen S, Denmark, within the SAS Drug Development system. The investigator will also receive a copy of the trial site's final and locked data (including audit trail, electronic signature and queries) as write-protected PDF files produced by the independent, third-party CRO. The PDF files will be stored on a CD and will be provided to the investigator before access to the eCRF is revoked. The Investigator will approve/authorise the eCRF entries for each subject with an electronic signature which equals a handwritten signature. Trial data will be entered into the system in a timely manner.

Errors occurring in the eCRF will be corrected electronically. Such corrections/modifications will be automatically tracked by an audit trail detailing the date and time of the correction and the name of the person making the correction.

10.3 Data Management

All data management activities will be specified in a Data Management Plan prepared under the responsibility of Global Biometrics, Ferring Pharmaceuticals A/S. All data management activities will be performed by independent, third-party CRO, under the responsibility of Global Biometrics, Ferring Pharmaceuticals A/S. A study database will be created according to the Data Management standard operating procedures and data validation programmes will be developed to check for data completion and validity.

Laboratory data will be transferred electronically to independent, third-party CRO for inclusion in the study data base according to laboratory data transfer specifications to be agreed between the individual laboratories and independent, third-party CRO. For medical coding of AEs, medical history and concomitant medication the most recent versions of MedDRA and WHO-Drug will be used. The coding will be performed by the third-party CRO and will be reviewed and approved by Ferring. When all data have been processed, queries resolved, medical coding completed and any issues from review of protocol violations and data listings resolved, the database will be locked and any further update will be denied. A final quality assurance audit of the locked database will take place prior to transfer of the final database structured according to Ferring's data transfer specifications.

10.4 Provision of Additional Information

On request, the investigator will provide Ferring with additional data relating to the trial, duly anonymized and protected in accordance with applicable requirements.

11 MONITORING PROCEDURES

11.1 Periodic Monitoring

The monitor will contact and visit the investigator periodically to ensure adherence to the protocol, ICH-Good Clinical Practice (ICH-GCP), standard operating procedures and applicable regulatory requirements, maintenance of trial-related source records, completeness, accuracy and verifiability of eCRF entries compared to source data, verification of drug accountability, and compliance with safety reporting instructions.

The investigator will permit the monitor direct access to all source data, including electronic medical records, and/or documents in order to facilitate data verification. The investigator will cooperate with the monitor to ensure that any discrepancies that may be identified are resolved. The investigator is expected to meet the monitor during these visits.

When the first subject is randomized at the trial site, a monitoring visit will take place shortly thereafter. For this trial, the frequency of the interim monitoring visits will be determined by the enrollment rate and will be detailed in the monitoring plan.

11.2 Audit and Inspection

The investigator will make all the trial-related source data and records available at any time to quality assurance auditor(s) mandated by Ferring or to domestic/foreign regulatory inspectors or representatives from IEC(s)/IRB(s) who may audit/inspect the trial. The main purposes of an audit or inspection are to assess compliance with the trial protocol and the principles of ICH-GCP, including the Declaration of Helsinki and all other relevant regulations.

The subjects must be informed by the investigator and in the informed consent documents that authorized Ferring representatives and representatives from regulatory authorities and IEC(s)/IRB(s) may wish to inspect their medical records. During audits/inspections, the auditors/inspectors may copy relevant parts of the medical records. No personal identification other than the screening/randomization number will appear on these copies.

The investigator should notify Ferring without any delay of any inspection by a regulatory authority or IEC/IRB.

